10.3. Criteria for Potential Clinical Significant Abnormalities (PCSA)

Parameter	PCSA	Comments
Clinical Chemistry		
ALT	By distribution analysis : Enzymes activities must be expressed in ULN, not in IU/L. >3 ULN >5 ULN >10 ULN >20 ULN	Concept paper on DILI – FDA draft Guidance Oct 2007. Internal DILI WG Oct 2008. Categories are cumulative. First row is mandatory. Rows following one mentioning zero can be deleted.
AST	By distribution analysis : Enzymes activities must be expressed in ULN, not in IU/L. >3 ULN >5 ULN >10 ULN >20 ULN	Concept paper on DILI – FDA draft Guidance Oct 2007. Internal DILI WG Oct 2008. Categories are cumulative. First row is mandatory. Rows following one mentioning zero can be deleted.
Alkaline Phosphatase	>1.5 ULN	Enzymes activities must be expressed in ULN, not in IU/L. Concept paper on DILI – FDA draft Guidance Oct 2007. Internal DILI WG Oct 2008.
Total Bilirubin	>1.5 ULN >2 ULN	Must be expressed in ULN, not in $\mu\text{mol}/\text{L}$ or mg/L . Categories are cumulative. Concept paper on DILI – FDA draft Guidance Oct 2007. Internal DILI WG Oct 2008.
Conjugated Bilirubin	>35% Total Bilirubin and TBILI>1.5 ULN	Conjugated bilirubin dosed on a case-by-case basis.
ALT and Total Bilirubin	ALT>3 ULN and TBILI>2 ULN	Concept paper on DILI – FDA draft Guidance Oct 2007. Internal DILI WG Oct 2008. To be counted within a same treatment phase, whatever the interval between measurement.
CPK	>3 ULN >10 ULN	FDA Feb 2005. Am J Cardiol April 2006. Categories are cumulative. First row is mandatory. Rows following one mentioning zero can be deleted.

Parameter	PCSA	Comments
Creatinine	$\geq 150 \text{ } \mu\text{mol/L}$ (Adults) $\geq 30\%$ change from baseline $\geq 100\%$ change from baseline	Benichou C., 1994.
CLcr (mL/min) (Estimated creatinine clearance based on the Cockcroft-Gault equation)	$\geq 15 - < 30$ (severe decrease in GFR) $\geq 30 - < 60$ (moderate decrease in GFR) $\geq 60 - < 90$ (mild decrease in GFR) ≥ 90 (normal GFR)	Use is optional. FDA draft Guidance 2010 Pharmacokinetics in patients with impaired renal function-study design, data analysis, and impact on dosing and labeling
eGFR (mL/min/1.73m ²) (Estimate of GFR based on an MDRD equation)	$\geq 15 - < 30$ (severe decrease in GFR) $\geq 30 - < 60$ (moderate decrease in GFR) $\geq 60 - < 90$ (mild decrease in GFR) ≥ 90 (normal GFR)	Use is optional. FDA draft Guidance 2010 Pharmacokinetics in patients with impaired renal function-study design, data analysis, and impact on dosing and labeling
Uric Acid		Harrison- Principles of Internal Medicine 17 th Ed., 2008.
Hyperuricemia	$> 408 \text{ } \mu\text{mol/L}$	
Hypouricemia	$< 120 \text{ } \mu\text{mol/L}$	
Blood Urea Nitrogen	$\geq 17 \text{ mmol/L}$	
Chloride	$< 80 \text{ mmol/L}$ $> 115 \text{ mmol/L}$	
Sodium	$\leq 129 \text{ mmol/L}$ $\geq 160 \text{ mmol/L}$	
Potassium	$< 3 \text{ mmol/L}$ $\geq 5.5 \text{ mmol/L}$	FDA Feb 2005.
Lipasemia	$\geq 3 \text{ ULN}$	
Amylasemia	$\geq 3 \text{ ULN}$	
Glucose		
Hypoglycaemia	$\leq 3.9 \text{ mmol/L}$ and $< \text{LLN}$	ADA May 2005.
Hyperglycaemia	$\geq 11.1 \text{ mmol/L}$ (unfasted); $\geq 7 \text{ mmol/L}$ (fasted)	ADA Jan 2008.

Parameter	PCSA	Comments
HbA1c	>8%	
Albumin	≤25 g/L	
CRP	>2 ULN or >10 mg/L (if ULN not provided)	FDA Sept 2005.
Hematology		
WBC	<3.0 Giga/L (Non-Black); Increase in WBC: not relevant. <2.0 Giga/L (Black) ≥16.0 Giga/L	To be interpreted only if no differential count available.
Lymphocytes	>4.0 Giga/L	
Neutrophils	<1.5 Giga/L (Non-Black); <1.0 Giga/L (Black)	International Consensus meeting on drug-induced blood cytopenias, 1991. FDA criteria.
Monocytes	>0.7 Giga/L	
Basophils	>0.1 Giga/L	
Eosinophils	>0.5 Giga/L or >ULN (if ULN ≥ 0.5 Giga/L)	Harrison- Principles of internal Medicine 17 th Ed., 2008.
Hemoglobin	≤115 g/L (Male); ≤95 g/L (Female) ≥185 g/L (Male); ≥165 g/L (Female)	Criteria based upon decrease from baseline are more relevant than based on absolute value. Other categories for decrease from baseline can be used (≥30 g/L, ≥40 g/L, ≥50 g/L).
Decrease from Baseline ≥20 g/L		
Hematocrit	≤0.37 v/v (Male) ; ≤0.32 v/v (Female) ≥0.55 v/v (Male) ; ≥0.5 v/v (Female)	
RBC	≥6 Tera/L	Unless specifically required for particular drug development, the analysis is redundant with that of Hb. Otherwise, consider FDA criteria.
Platelets	<100 Giga/L ≥700 Giga/L	International Consensus meeting on drug-induced blood cytopenias, 1991.

Parameter	PCSA	Comments
Urinalysis		
pH	≤ 4.6 ≥ 8	
Vital signs		
HR	≤ 50 bpm and decrease from baseline ≥ 20 bpm ≥ 120 bpm and increase from baseline ≥ 20 bpm	To be applied for all positions (including missing) except STANDING.
SBP	≤ 95 mmHg and decrease from baseline ≥ 20 mmHg ≥ 160 mmHg and increase from baseline ≥ 20 mmHg	To be applied for all positions (including missing) except STANDING.
DBP	≤ 45 mmHg and decrease from baseline ≥ 10 mmHg ≥ 110 mmHg and increase from baseline ≥ 10 mmHg	To be applied for all positions (including missing) except STANDING.
Orthostatic Hypotension		
Orthostatic SDB		
Orthostatic DBP	≤ -20 mmHg ≤ -10 mmHg	
Weight	$\geq 5\%$ increase from baseline $\geq 5\%$ decrease from baseline	FDA Feb 2007.
ECG		
		Ref.: CPMP 1997 guideline.
HR	≤ 50 bpm and decrease from baseline ≥ 20 bpm ≥ 120 bpm and increase from baseline ≥ 20 bpm	
PR	≥ 220 ms and increase from baseline ≥ 20 ms	
QRS	≥ 120 ms	

Parameter	PCSA	Comments
QTc	Absolute values (ms)	To be applied to any kind of QT correction formula.
Borderline		
Prolonged*	Borderline: 431-450 ms (Male); 451-470 ms (Female)	
Additional	Prolonged: >450 ms (Male); >470 ms (Female) ≥500 ms	*QTc prolonged and Δ QTc>60 ms are the PCSA to be identified in individual subjects/patients listings.
	Increase from baseline	
	Borderline: Increase from baseline 30-60 ms	
	Prolonged: Increase from baseline >60 ms	

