4.2.1. Inclusion Criteria

A patient must meet the following criteria to be eligible for inclusion in the study:

1. Men and women \geq age 40 and \leq age 85
2. Patients with heFH (see [Appendix 1](#) and [Appendix 2](#) for diagnosis criteria) or non-FH patients at high or very high cardiovascular risk

High and very high cardiovascular risk patients include patients with coronary heart disease (CHD), non-CHD CVD, and other risk factors. Definitions for CHD, non-CHD CVD, and other risk factors:

- a. A documented history of CHD (includes 1 or more of the following):
 - i. Acute myocardial infarction
 - ii. Silent myocardial infarction
 - iii. Unstable angina
 - iv. Coronary revascularization procedure (eg, percutaneous coronary intervention or coronary artery bypass graft surgery)
 - v. Clinically significant CHD diagnosed by invasive or non-invasive testing (eg, coronary angiography, stress test using treadmill, stress echocardiography, coronary calcium scan, or nuclear imaging).
- b. Non-CHD CVD (includes 1 or more of the following criteria):
 - vi. Documented previous ischemic stroke with a focal ischemic neurological deficit that persisted more than 24 hours, considered as being of atherothrombotic origin. Computed tomography (CT) or magnetic resonance

imaging (MRI) must have been performed to rule out hemorrhage and non-ischemic neurological disease.

- vii. Peripheral arterial disease
- viii. Abdominal aortic aneurysm
- ix. Atherosclerotic renal artery stenosis
- x. Carotid artery disease (transient ischemic attacks or >50% obstruction of a carotid artery)

c. Other risk factors

- xi. Documented moderate chronic kidney disease as defined by $30 \leq$ Estimated Glomerular Filtration Rate (eGFR) <60 mL/min/1.73 m² for 3 months or more, including the screening visit
- xii. Type 1 or type 2 diabetes mellitus
- xiii. A calculated 10-year fatal CVD risk SCORE $\geq 5\%$ (ESC/EAS Guidelines for the management of dyslipidemias, [Perk 2012](#))

* For CVD risk categories, see [Appendix 5](#).

3. Patients with history of CHD not having adequate control of their hypercholesterolemia with LDL-C ≥ 70 mg/dL, or all other patients with LDL-C ≥ 100 mg/dL

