6.3. General Data Handling Conventions

In general, the following formulas will be used for computation of parameters:

Time from diagnosis

Time from diagnosis (years) = (Date of informed consent – Date of diagnosis*) / 365.25.

(*):In case the month of diagnosis would be missing, it will be put equal to JANUARY if the year of diagnosis equals the year of informed consent; it will be put equal to JUNE otherwise. In the case the day is missing, the day will be put equal to 1st if the month and year of diagnosis equals the month and year of informed consent; otherwise it will be put equal to the 15th of the month.

Date of last dose of study treatment

The date of the last injection is equal to the last date of administration reported on injection administration case report form page, or missing if the last administration date is unknown.

Renal function formulas

Estimated GFR will be derived using the Modification of the Diet in Renal Disease (MDRD) equation:

$186.3 \times (\text{creatinine in } \mu\text{mol/L} / 88.4)^{-1.154} \times (\text{age in years})^{-0.203} \times 0.742 \text{ if female, } \times 1.21 \text{ if race is "black or African American".}$

Lipids variables, laboratory safety variables, hs-CRP

For data below the lower limit of quantification (LLOQ) / limit of linearity, half of the lower limit value (i.e., LLOQ/2) will be used for quantitative analyses. For data above the upper limit of quantification (ULOQ) / limit of linearity, the upper limit value (i.e., ULOQ) will be used for quantitative analyses.

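### The optional creatinine-clearance and eGFR rows in SAP 10.3 have no category below 15, so the lowest values go ungraded there, although the creatinine row still flags every eGFR below 15

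*SAP*

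**What the plan says.** SAP 10.3 (criteria for potentially clinically significant abnormalities, PCSA) has two filtration rows. One is CLcr, described as "Estimated creatinine clearance based on the Cockcroft-Gault equation"; the other is eGFR by an MDRD equation. Both print the same four bands. The lowest is "\geq 15 - < 30$ (severe decrease in GFR"), followed by 30 to <60 (moderate), 60 to <90 (mild) and "≥ 90 (normal GFR"). The comment on both rows is "Use is optional". The ALT, AST, total bilirubin and CPK rows are marked as cumulative; these two are not.

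The same table has a creatinine row with no optional label. Its limits are 150 µmol/L or more, a change of at least 30%, and "\geq 100\%$ change from baseline".

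Elsewhere:
- SAP 4.7.2 lists creatinine clearance among the renal parameters to be analysed.
- SAP 6.3 says "Estimated GFR will be derived using the Modification of the Diet in Renal Disease (MDRD) equation" and prints the formula. It prints no formula for CLcr.
- SAP 5.7.2 counts a patient when at least one post-baseline value in the TEAE period meets a criterion, and lists the values that do. It allows normal-range tables as a substitute only for parameters that have no PCSA criteria.
- Protocol 4.2.1 admits patients with "Documented moderate chronic kidney disease as defined by" an eGFR of 30 to <60, and patients with diabetes. Protocol 4.2.2 excludes an eGFR below 30.

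**The concern.** Because the rows include a normal band and are not cumulative, they work as a classification scale, and such a scale should place every possible value. This one is open at the top and closed at the bottom. Under the SAP 5.7.2 counting rule, a value below 15 meets no GFR criterion. It is neither counted nor listed under GFR, while a milder value of 15 to <30 is counted as severe. The normal-range substitute does not help, since GFR does have criteria.

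Such values can occur. Moderate kidney disease and diabetes are qualifying conditions, patients enter up to age 85, and follow-up is 96 weeks. Scheduled post-baseline chemistry is at weeks 24, 48, 72 and 96 only (Protocol Table 1), so a patient could pass through 15 to <30 without a sample. At stake is a correct count by arm of the most severe GFR category in a descriptive safety table.

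**Working it through.** The plan states no figure on this point to reproduce. The check is to classify values with the printed bands, then see what the creatinine row catches.

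**1. Classification with the printed bands**

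| Value | Band |
|---|---|
| 5, 10, 14.9 | none |
| 15, 29.9 | severe |
| 30, 59.9 | moderate |
| 60 | mild |
| 90, 120 | normal |

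**2. Creatinine at eGFR 15.** SAP 6.3 gives eGFR = 186.3 × (Cr/88.4)^−1.154 × age^−0.203, × 0.742 if female, × 1.21 if black. Solving for creatinine:

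Cr = 88.4 × (186.3 × age^−0.203 × sex term × race term / eGFR)^(1/1.154)

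Ages run from 40 (entry minimum) to 87 (entry maximum of 85 plus about two years in the study).
- Lowest case, non-black woman aged 87: 186.3 × 0.4039 × 0.742 / 15 = 3.722; 3.722^(1/1.154) = 3.123; × 88.4 = **276 µmol/L**.
- Highest case, black man aged 40: 186.3 × 0.4729 × 1.21 / 15 = 7.107; 7.107^(1/1.154) = 5.471; × 88.4 = **484 µmol/L**.

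Creatinine rises as eGFR falls, so every eGFR below 15 lies above 276 µmol/L and meets the 150 µmol/L limit.

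**3. Change limits.** For one patient, the creatinine ratio is (eGFR before / eGFR after)^(1/1.154), ignoring ageing during the study.
- From the entry limit of 30 to 15: 2^(1/1.154) = 1.82, a rise of 82%. The 30% limit is met.
- The 100% limit is met at eGFR 15 when baseline is at least 15 × 2^1.154 = **33.4**. Only baselines of about 30 to 33.4 could miss it, and they still meet the other two limits.

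**4. Whether creatinine can stand in for the missing grade**
- Fall from 90 to 40: (90/40)^(1/1.154) = 2.02.
- Fall from 40 to 10: (40/10)^(1/1.154) = 3.32.

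Both meet the 30% and the 100% limit, and there is no higher one. The absolute limit does not separate them either. In a non-black man aged 65, a creatinine of 150 µmol/L is an eGFR of 43.4. His creatinine is therefore 150 × (43.4/40)^(1/1.154) ≈ 161 µmol/L at eGFR 40, and 161 × 3.32 ≈ 535 µmol/L at eGFR 10. Both exceed 150. SAP 5.7.2 splits the counts by baseline PCSA status, which would put these two falls in different strata for the absolute limit, but that shows where each started and not how low each ended.

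**5. Limit of the check.** Steps 2 to 4 concern MDRD eGFR. The SAP prints no Cockcroft-Gault formula, so the same assurance is not derived for CLcr.

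**The case against.** The strongest reply is that nothing of substance is lost. The creatinine row is not optional, and it catches every eGFR below 15. A fall from 40 to 10 meets all three creatinine limits, including the highest. This stands for detection; by step 4 it does not stand for grading.

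Second, the rows are optional. The appendix is a general sponsor list (SAP 5.7 dates it January 2009), and it also carries ECG, lipase and amylase rows that match nothing in the schedule of events or the laboratory lists. Presence in the appendix does not prove that a GFR table will be produced. This stands, and it makes the point conditional. But the SAP lists creatinine clearance for analysis, prints the eGFR formula, and nowhere says that the rows will be dropped.

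Third, other displays would show the case: minimum by visit, last and worst on-treatment values, the blood urea nitrogen criterion, and adverse event reporting. This stands in part. None of these is a count by arm of patients below 15, and the worst-value summaries stop 21 days after the last dose while PCSA counts run to 70 days.

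Fourth, a reader might infer that a patient who falls from 40 to 10 is recorded with no GFR abnormality. The documents do not support that as a general statement. One qualifying post-baseline value is enough, and unscheduled and repeat values count. An earlier post-baseline reading of 40 is counted as moderate, and any reading of 15 to <30 as severe. The patient is absent from every GFR band only if all post-baseline values in the TEAE period are below 15.

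**Conclusion.** The gap is real and minor. If the CLcr and eGFR rows are used as printed, values below 15 are counted in no GFR band while less severe values are, so the scale gives a wrong count at its worst end.

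A reader might go further and infer that the worst renal outcome is missing from the PCSA table altogether. It is not: by the SAP's formula, every eGFR below 15 meets the creatinine limit of 150 µmol/L, and the creatinine value would appear in the PCSA listings. The loss is confined to the count and grading in the lowest GFR category.

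Few patients should be affected, since an eGFR of at least 30 is needed at entry. The documents give no rate of decline to below 15, so no patient number is offered. The primary analysis and all formal inference are unaffected. The conclusion assumes that the optional rows are used, that baseline eGFR is at or above the entry limit, and that both rows are complete as read. They show the same four bands, which makes a lost line unlikely.

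**What to change.** In SAP 10.3, add an open-ended <15 category to both the CLcr and the eGFR row. Alternatively, make the lowest band <30 and add <15 as a cumulative sub-row, labelled as such. It would also help to state whether the two optional rows will be used.

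The cost is about one line per row in the appendix and the matching table shell, made before database lock. Data collection, patient management and inference do not change. Tabulating the worst category against the baseline category is an optional layout choice and not part of this correction.

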10.4. List of MedDRA terms for CMQs

Table 5: Selected PTs from SMQ “Optic nerve disorders” including in the CMQ for neurologic events

MedDRA Term Label
Benign neoplasm of optic nerve
Optic atrophy
Optic discs blurred
Optic nerve disorder
Optic nerve injury
Optic nerve neoplasm
Optic nerve operation
Optic neuropathy
Papillitis
Pseudopapilloedema
Subacute myelo-opticoneuropathy
Toxic optic neuropathy
Visual evoked potentials abnormal
Amaurosis fugax
Blindness
Blindness unilateral
Colour blindness acquired
Colour vision tests abnormal
Cranial nerve injury
Delayed myelination

MedDRA Term Label
Fundoscopy abnormal
Hemianopia
Hemianopia heteronymous
Hemianopia homonymous
Loss of visual contrast sensitivity
Neuro-ophthalmological test abnormal
Night blindness
Ophthalmological examination abnormal
Optic pathway injury
Optical coherence tomography abnormal
Quadrantanopia
Visual acuity reduced
Visual acuity reduced transiently
Visual acuity tests abnormal
Visual field defect
Visual field tests abnormal
Visual impairment
Visual pathway disorder

Table 6: CMQ “Neurocognitive disorders – FDA’s recommendation”

MedDRA level	MedDRA Term Label
PTCD	Amnesia
PTCD	Amnestic disorder
PTCD	Anterograde Amnesia
PTCD	Neuropsychiatric symptoms
PTCD	Change in sustained attention
LLTCD	Cognitive Deterioration
PTCD	Cognitive Disorder
LLTCD	Confusion
LLTCD	Confusion Aggravated
PTCD	Confusional State
PTCD	Delirium
PTCD	Dementia
PTCD	Dementia Alzheimer's type
LLTCD	Dementia Nos
LLTCD	Dementia Nos Aggravated
LLTCD	Dementia of the Alzheimer's type NOS
PTCD	Dementia with Lewy Bodies
PTCD	Disorientation
PTCD	Disturbance in attention
PTCD	Executive dysfunction
PTCD	Frontotemporal Dementia
LLTCD	Global Amnesia

MedDRA level	MedDRA Term Label
PTCD	Illogical Thinking
PTCD	Impaired reasoning
PTCD	Incoherent
PTCD	Judgement impaired
PTCD	Memory Impairment
PTCD	Mental Impairment
LLTCD	Mental Impairment Nos
LLTCD	Mental State Abnormal Aggravated
PTCD	Mental Status Changes
PTCD	Mini Mental Status Examination Abnormal
PTCD	Presenile Dementia
PTCD	Retrograde Amnesia
PTCD	Senile Dementia
LLTCD	Senile Dementia Nos
LLTCD	Short-term Memory Loss
PTCD	Thinking Abnormal
LLTCD	Thinking Slowed
PTCD	Transient Global Amnesia
PTCD	Vascular Dementia

Table 7: CMQ “Type 1 or Type 2 diabetes”

MedDRA Term Label	Preferred Term Code
Diabetes mellitus	10012601
Diabetes mellitus inadequate control	10012607
Insulin resistant diabetes	10022491
Diabetes mellitus malnutrition-related	10050197
Diabetes mellitus management	10051599
Insulin-requiring type 2 diabetes mellitus	10053247
Type 1 diabetes mellitus	10067584
Type 2 diabetes mellitus	10067585
Fulminant type 1 diabetes mellitus	10072628

10.5. Detailed Description of the Multiple Imputation Procedure

The following is a detailed description of the multiple imputation procedure which will be used for sensitivity analysis of primary endpoint as well as the analysis of the secondary endpoints.

In general, the missing pattern is anticipated to be not monotone, a two-step approach will be used:

- Step 1: the MCMC method will be used in conjunction with the IMPUTE=MONOTONE option to create an imputed data set with a monotone missing pattern.

- Step 2: Using the monotone data set from step 1, missing data will be imputed using the regression method.

The imputation model for step 1 will include the treatment group and the values of the analyzed parameter at baseline and planned time-points up to week 96.

The imputation model for step 2 will include the same variables as in step 1 with the following additional variables:

- the randomization strata (age and statin use strata);
- age, BMI, and gender (age and BMI included as continuous variables).

Non-continuous variables included in the imputer's model (i.e., treatment group, randomization strata and gender) are not expected to be missing.

In addition, for continuous efficacy variables anticipated to have a non-normal distribution (i.e. TG and Lp(a)), data will be log-transformed before imputation process and then back-transformed to create the imputed data sets using the TRANSFORM statement of SAS MI procedure.

For variables other than those continuous efficacy variables anticipated to have a non-normal distribution (i.e. TG and Lp(a)), for each simulation leading to negative imputed value, another value will be redrawn using MINIMUM option of MI SAS procedure.

The number of imputations (100) will be informally verified by replicating sets of 100 imputations and checking whether the combined results are stable. If not stable, the number of imputations will be increased and informally checked as above, and thus continued until stable estimates are obtained.

